1.2.4.6.4. Week 24 Conclusions

Key conclusions from the Week 24 analysis of Study GS-US-292-0102 included the following:

- The proportion of subjects with plasma HIV-1 RNA < 50 copies/mL at Week 24 was similar between treatment groups
- Treatment was generally well tolerated as most AEs were mild and not associated with treatment discontinuation. No new or unexpected adverse events occurred.
- The data shows that subjects taking E/C/F/TAF had more modest changes in creatinine and in bone mineral density than subjects taking E/C/F/TDF. The differences were statistically significant and may have important clinical relevance for individual subjects.

Other than renal lab abnormalities and biomarkers and bone biomarkers, the frequency and type of laboratory abnormalities was comparable between the two treatment arms.

1.3. Rationale for This Study

1.3.1. Tenofovir Alafenamide (TAF) for Treatment of Chronic Hepatitis B

Approximately one-third of the world's population has serological evidence of past or present HBV infection with over 350 million people globally who are chronic HBV surface antigen (HBsAg) carriers. The disease burden for HBV varies regionally, with greater than 50% of all subjects residing in Asian countries with the highest prevalence (e.g. China, India, Vietnam, Indonesia, South Korea, Taiwan, the Philippines, and Pakistan). The primary goal of treatment is to achieve and maintain virologic suppression, without resistance, which has been shown to

translate to improvement in liver disease outcomes. Current guidelines recommend treatment for subjects with evidence of ongoing viral replication along with liver injury based on elevated levels of serum ALT.

TDF and ETV are highly potent first line therapies for CHB; however, each has specific limitations. TDF has a potential to cause renal- and bone-related toxicities in a subset of subjects. ETV has reduced activity in drug-treated populations, specifically lamivudine-experienced/resistant subjects {[Baldick et al 2008](#), [Tenney et al 2009](#)}. The latter is a key limitation for ETV use as LAM remains one of the most commonly prescribed HBV treatments in most regions of the world. Thus, despite the availability of effective treatments there remains a clear need for newer oral HBV agents that are safe and well tolerated for long term use, and capable of achieving high rates of viral suppression with little or no potential for resistance development.

Tenofovir alafenamide (TAF), a novel prodrug of TFV, has the potential to further advance the treatment of chronic HBV infection. In contrast to TDF, an agent that is rapidly and completely cleaved by intestinal and plasma esterases to TFV, TAF is a more stable prodrug that efficiently resists early enzymatic cleavage following oral administration and remains more fully intact until it is taken up by target cells. As a consequence, TAF, when given at a lower dose than TDF, is capable of efficiently delivering active drug (e.g. TFV-DP) to the virally-infected cells (e.g. HBV-infected hepatocytes and HIV-infected lymphoid cells) while systemic exposures of TFV are reduced compared with oral administration of TDF 300 mg. These features are hypothesized to translate into the potential for effective suppression of viral replication, and an improved tolerability and safety profile.

Results from GS-US-320-0101, a Phase 1b study evaluating the short-term (28 day) safety, efficacy (HBV DNA suppression), and PK of TAF at 4 dose levels (8 mg, 25 mg, 40 mg, and 120 mg) compared to TDF 300 mg, has shown no dose effect in regard to viral suppression, and similar short-term safety and tolerability compared with TDF. Intensive PK results show 93% or greater reductions in TFV exposures with doses of TAF 25 mg or lower compared to the TFV exposures generated with TDF 300 mg. These results, taken together with 24 weeks safety results from the HIV Phase 2 study GS-US-292-0102, which directly compares TAF to TDF (each included as a component of an STR), suggest that TAF is safe and well tolerated and may have a lower potential for renal- and bone-related AEs compared to TDF. Importantly, TFV exposures for E/C/F/TAF 10 mg are comparable to TFV exposures generated with TAF 25 mg given as a stand alone agent.

1.3.2. Rationale for the Current Study

TDF and ETV are highly potent first line therapies for chronic HBV; however, each has specific limitations. TDF has a potential to cause renal- and bone-related toxicities in a subset of subjects. ETV has reduced activity in drug-treated populations, specifically lamivudine (LAM)-experienced/resistant subjects. Thus, despite the availability of effective treatments there remains a clear need for newer oral HBV agents that are safe and well tolerated for long term use, and capable of achieving high rates of viral suppression with little or no potential for resistance development. TAF has the potential to address each of these requirements.

The current study is designed to evaluate non-inferiority of TAF compared to TDF in regard to the proportion of subjects with HBV DNA levels below 29 IU/mL at Week 48. The durability of TAF compared to TDF in regard to the proportion of subjects with HBV DNA < 29 IU/mL at Weeks 96 and 144 will also be assessed in a double blind fashion. In addition to treatment naïve subjects, treatment experienced CHB subjects who are viremic and with elevated ALT levels at screening are included. This is based on given results from GS-US-174-0106 (ADV suboptimal responders) and GS-US-174-0121 (LAM-resistant subjects) which demonstrated in viremic patients comparable rates of HBV DNA suppression, as described below, in comparison to results in mostly treatment naïve subjects participating in pivotal studies GS-US-174-0102 (HBeAg-negative subjects) and GS-US-174-0103 (HBeAg-positive subjects). Given the unique properties of TAF (efficient delivery of the active moiety, TFV-DP, to HBV-infected hepatocytes with reduced systemic TFV exposures), this study will also evaluate the potential safety differences (e.g. renal- and bone-related complications) of TAF relative to TDF at Week 48 and long term comparative safety at Week 96 and 144, after which subjects will be further evaluated for longer-term safety and efficacy of TAF in an open-label TAF 25 mg QD extension phase through Week 384. The extension phase is important as it will enable the evaluation of subjects treated for the entire 384 week period with TAF as well as those who received 144 weeks of TDF initially in a double-blinded fashion followed by an additional 240 weeks of open-label TAF. The latter group will allow an ongoing assessment, including possible resolution, of any potential bone- and/or renal-related (or other) complications during TAF treatment that might have arisen under initial treatment with TDF.

The primary endpoint of this study is the proportion of subjects with HBV DNA < 29 IU/mL at Week 48; the lowest limit of susceptibility of the polymerase chain reaction (PCR) assay to be employed (Roche COBAS® Taqman® HBV test for use with the High Pure System). A histological component of treatment response is not included. Alternatively, non-invasive means (i.e. Fibrotest®) will be used to assess the degree of fibrosis at baseline and the change in fibrosis on an annual basis for all subjects participating in the trial. In support of this, 48 week results from studies, GS-US-174-0102 and GS-US-174-0103, which formed the basis for TDF approval for CHB, showed TDF to be superior to ADV based on a “complete response” to treatment (a composite endpoint of HBV DNA suppression and histologic improvement based on repeat liver biopsy). In GS-US-174-0102, conducted in HBeAg-negative (presumed pre-core mutant) subjects, 70.8% and 48.8% of subjects randomized to TDF and ADV, respectively, achieved a complete response at Week 48 (treatment difference: 23.5%; $p < 0.001$). Of the components, HBV DNA suppression (< 69 IU/mL) was achieved in 94.4% and 64.0% (treatment difference: 30.3%; $p < 0.001$), while histologic improvement was achieved in 74.2% and 68.8% (treatment difference: 5.2%; $p = 0.292$) of TDF- and ADV-treated subjects, respectively. Thus, the greater potency of TDF relative to ADV resulting in a significantly higher rate of viral suppression was the primary element associated with the superior treatment response at 48 weeks {[Marcellin et al 2007](#), [Marcellin et al 2008](#)}. Similar findings were observed in HBeAg-positive subjects in GS-US-174-0103.

After 48 weeks, subjects in GS-US-174-0102 and GS-US-174-0103 were eligible to continue open-label treatment with TDF. At Year 5 (Week 240), 331/641 (52%) of subjects on TDF (without addition of FTC) underwent a repeat liver biopsy, and regression of fibrosis

(improvement in Ishak fibrosis score of ≥ 1 point) was seen in 52% (172/331) of subjects. Furthermore, in 94/331 (28%) subjects with cirrhosis (Ishak score ≥ 5) at baseline, 73% (69/94) were no longer cirrhotic at year 5 (≥ 1 unit decrease in Ishak score). These results confirm the benefits of long term viral suppression with TDF in terms of regression of fibrosis and reversal of cirrhosis in the majority of TDF-treated subjects {[Marcellin et al 2013](#)}.

The efficacy of TDF in viremic treatment experienced CHB populations has been shown to be similar to treatment naïve subjects. In a prospective, randomized (1:1), double-blind, Phase 3b study (GS-US-174-0121) which compared TDF alone to the combination of FTC/TDF in 280 HBeAg-positive and HBeAg-negative subjects receiving treatment with LAM and having HBV DNA $> 3 \log_{10}$ IU/mL with documented LAM-resistance (rtM204I/V \pm rtL180M mutation[s]), 89.4% of TDF-treated subjects vs. 86.3% treated with FTC/TDF had HBV DNA < 69 IU/mL at Week 96 (primary endpoint, missing equals failure analysis; $p = 0.43$). BMD was also assessed in GS-US-174-0121, and small declines in BMD ($< 2\%$) of both hip and spine were seen with equal frequency in both groups which occurred by Week 24 (spine) and Week 72 (hip). In another prospective, randomized, double-blind study of TDF vs. FTC/TDF in 105 HBeAg-positive and HBeAg-negative subjects with a prior suboptimal response to ADV (GS-US-174-0106), no differences in HBV DNA suppression (proportion less than 69 IU/mL) were seen between treatment groups (82.4% TDF vs. 84.0% FTC/TDF; ITT, non-completer equals failure; $p = 0.78$). Taken together, these studies support the efficacy of TDF in treatment experienced subjects as being similar to results seen in treatment naïve subjects.

1.3.3. Rationale for Dose Selection

In the Phase 1b study, GS-US-320-0101, which has completed enrollment, 4 doses (8, 25, 40, and 120 mg) of TAF monotherapy, and TDF 300 mg were evaluated in 51 treatment naïve CHB subjects. To date, all subjects have completed the 28 day dosing period. Results demonstrate that TAF when given in doses over a range of 8 to 120 mg results in similar HBV DNA declines over 28 days. Furthermore, HBV DNA suppression with TAF is comparable to that of TDF 300 mg. In GS-US-320-0101, increased rates of viral suppression were not observed with higher TAF doses (40 mg, 120 mg) relative to lower TAF doses (8 mg and 25 mg), and similar safety profiles were observed among TAF treatment groups. PK results demonstrate a 93% reduction in TFV exposures relative to TDF 300 mg when TAF is dosed at 25 mg. These results in CHB subjects are consistent with data in healthy volunteers and HIV-infected subjects given TAF 25 mg as a stand alone agent. Importantly, as previously stated, the TFV exposures seen with TAF 25 mg in CHB subjects are therapeutically comparable to those in HIV patients receiving E/C/F/TAF 10 mg (due to an inhibitory drug-drug interaction between TAF and COBI when these agents are included in the E/C/F/TAF STR) which provide safety data (from Phase 2 study GS-US-292-0102) supporting the development of TAF for hepatitis B at the 25 mg dose level. Further, in CHB subjects participating in the Phase 1b study who were dosed at the lowest TAF dose (8 mg), a 97% reduction in TFV exposures relative to TDF 300 mg was observed, representing an incremental reduction in TFV exposure of only 5% at this dose level relative to TAF 25 mg.

Importantly, the TFV exposures at a 25 mg dose when given alone are consistent with TAF exposures generated with the E/C/F/TAF 10 mg STR currently in Phase 3 development for treatment of HIV infection. Thus, the efficacy and safety of TAF in HIV is also being evaluated at a dose level that is therapeutically equivalent to the dose selected for study GS-US-320-0108.

Final Week 24 results from GS-US-292-0102, a phase 2 study being conducted in HIV-1 treatment naïve subjects, demonstrated similar safety and tolerability of TAF vs. TDF when each is included as a component of STRs containing elvitegravir, cobicistat, and emtricitabine. At Week 24, significant differences were noted between arms in regard to smaller declines in hip BMD, estimated CL_{Cr} (Cockcroft-Gault), and changes in various biomarkers of bone and renal function which are suggestive of differences in bone and renal tolerability of TAF vs. TDF. Similar assessments are included in the present trial in HBeAg-negative, chronic HBV subjects, and the study is sufficiently powered to demonstrate a potentially superior safety profile for TAF relative to TDF in regard to these bone and renal parameters.

In summary, a 25 mg dose was selected for TAF for use in this non-inferiority trial based upon the safety profile for TAF in treatment naïve HIV-1-infected subjects from GS-US-292-0102, which utilizes a therapeutically equivalent TAF dose (10 mg as a component of the E/C/F/TAF STR), the viral suppression results in chronic HBV subjects in GS-US-320-0101 showing comparable rates of HBV DNA decline for a TAF 25 mg dose compared to TDF 300 mg (the approved dose for treatment of HBV), and the reduced systemic TFV exposures (~93%) seen with TAF relative to TDF 300 mg, when dosed at this level.

1.4. Compliance

This study will be conducted in compliance with this protocol, Good Clinical Practice (GCP), and all applicable regulatory requirements.

2. OBJECTIVES

The primary objectives of this study are:

- To compare the efficacy of tenofovir alafenamide (TAF) 25 mg QD versus tenofovir disoproxil fumarate (TDF) 300 mg QD for the treatment of HBeAg-negative, chronic hepatitis B at Week 48 in treatment-naïve and treatment-experienced subjects. The primary efficacy parameter is the proportion of subjects with plasma HBV DNA levels below 29 IU/mL
- To compare the safety and tolerability of TAF 25 mg QD versus TDF 300 mg QD for the treatment of HBeAg-negative, chronic hepatitis B at Week 48 in treatment naïve and treatment experienced subjects

The key secondary safety objectives of the study are:

- To compare the safety of TAF 25 mg QD versus TDF 300 mg QD as determined by the percent change from baseline in hip and spine BMD at Week 48
- To compare the safety of TAF 25 mg QD versus TDF 300 mg QD as determined by the change from baseline in serum creatinine at Week 48

Other secondary objectives of this study are as follows:

- To compare the efficacy of TAF 25 mg QD versus TDF 300 mg QD for the treatment of HBeAg-negative, chronic hepatitis B in regard to the proportion of subjects with plasma HBV DNA levels below 29 IU/mL at Weeks 96 and 144
- To compare the efficacy of TAF 25 mg QD versus TDF 300 mg QD for the treatment of HBeAg-negative, chronic hepatitis B in regard to the proportion of subjects with plasma HBV DNA levels below 29 IU/mL (target not detected) at Weeks 48, 96, and 144
- To compare the biochemical (ALT normalization by central laboratory and AASLD criteria) response of TAF 25 mg QD versus TDF 300 mg QD for the treatment of HBeAg-negative, chronic hepatitis B at Weeks 48, 96, and 144
- To compare the serological response (loss of HBsAg with seroconversion to anti-HBs) of TAF 25 mg QD versus TDF 300 mg QD for the treatment of HBeAg-negative, chronic hepatitis B at Weeks 48, 96, and 144
- To compare the change in fibrosis as assessed by FibroTest[®] of TAF 25 mg QD versus TDF 300 mg QD for the treatment of HBeAg-negative, chronic hepatitis B at Weeks 48, 96, and 144

- To compare the incidence of drug resistant mutations of TAF 25 mg QD versus TDF 300 mg QD at Weeks 48, 96, and 144
- To compare the change from baseline in ophthalmologic findings by fundoscopic examination of TAF 25 mg QD versus TDF 300 mg QD at Weeks 24, 48, 72 , 96, and 144 (or ED visit if prior to Week 144 and more than 24 weeks since prior exam) in a subset of subjects
- To characterize the pharmacokinetics of TAF and tenofovir (TFV) and determine intracellular concentrations of tenofovir diphosphate (TFV-DP) within peripheral blood mononuclear cells (PBMC) in subjects receiving TAF or TDF
- To evaluate the comparative open-label efficacy, safety, and the incidence of drug resistance mutations of TAF 25 mg QD in subjects initially randomized to TAF 25 mg QD and in subjects sequentially treated with TDF 300 mg QD and then switched to open-label TAF 25 mg QD

3. STUDY DESIGN

3.1. Treatment Plan and Regimen

This is a randomized, double-blind, non-inferiority study to compare the antiviral activity of TAF 25 mg QD versus TDF 300 mg QD. Approximately three hundred ninety (390) subjects will be randomized in a 2:1 ratio (A:B) to the treatment arms for 144 weeks (96 weeks under Amendment 2.1), and will be stratified by plasma HBV DNA level ($< 7 \log_{10}$ IU/mL, $\geq 7 \log_{10}$ IU/mL - $< 8 \log_{10}$ IU/mL, $\geq 8 \log_{10}$ IU/mL) and oral antiviral treatment status (treatment-naïve vs. treatment-experienced).

For China, approximately 150 additional subjects will be randomized in a 2:1 ratio (A: B) to the treatment arms for 96 weeks, and will be stratified by plasma HBV DNA level ($< 7 \log_{10}$ IU/mL, $\geq 7 \log_{10}$ IU/mL - $< 8 \log_{10}$ IU/mL, $\geq 8 \log_{10}$ IU/mL) and oral antiviral treatment status (treatment-naïve vs. treatment-experienced).

If the subject is deemed ineligible for this study by HBV serology (i.e. HBeAg positive CHB), this information may be used to determine eligibility for GS-US-320-0110 (another Gilead Sciences Phase 3 study in HBeAg positive, CHB subjects; this study must also be IRB/EC approved at the participating center).

Treatment Arm A: 260 subjects TAF 25 mg QD and matched placebo of TDF 300 mg QD
Treatment Arm B: 130 subjects TDF 300 mg QD and matched placebo of TAF 25 mg QD

[figure not shown]
For China, approximately 150 additional subjects (100 in Treatment Arm A and 50 in Treatment Arm B) will be enrolled for local registration purposes.

Subjects with a history of or current diagnosis of compensated cirrhosis are eligible for enrollment. Acceptable diagnostic criteria for cirrhosis include a Metavir or Knodell fibrosis score ≥ 4 or Ishak fibrosis score ≥ 5 by liver biopsy, or previous Fibroscan result > 12 kPa (in countries where locally approved). Available information regarding the presence or absence of cirrhosis by these criteria will be captured in the electronic case report forms at Baseline, and any other time during the trial should an investigator opt to undertake additional studies. Importantly, the change in fibrosis as assessed by Fibrotest[®] will be performed in all subjects participating in the trial at Baseline, and annually thereafter through Week 384/ED.

The duration of double-blind treatment is 144 weeks (96 weeks under Amendments 2.1). At Week 144, all subjects remaining on blinded treatment will be switched to the open-label TAF 25 mg QD extension period for up to an additional 240 weeks (Week 144 through Week 384/ED). Subjects already assigned to open-label TAF 25 mg QD at Week 96 per Amendment 2.1 will continue on open-label TAF 25 mg QD through Week 384/ED. All subjects who complete the double-blind period of treatment are eligible for participation in the open label TAF 25 mg QD extension period. Subjects who permanently discontinue study drug (either prematurely [ED] or at the end of study [Week 384]) for reasons other than HBsAg loss with confirmed seroconversion to anti-HBs, will be followed every 4 weeks for 24 weeks off treatment or until initiation of alternative, commercially available HBV therapy, whichever occurs first.

Subjects with HBsAg loss with confirmed seroconversion to anti-HBs should discontinue study drug within 3-6 months following confirmation of seroconversion to anti-HBs. Subjects with HBsAg loss with confirmed seroconversion to anti-HBs prior to Week 48 are not permitted to discontinue study drug prior to the Week 48 visit. After Week 48, these subjects who discontinue study drug will be followed off treatment every 4 weeks for 12 weeks and then per the study visit schedule ([Appendix 2](#)) through Week 384/ED. Discontinuation of study drug for subjects experiencing HBsAg loss with confirmed seroconversion to anti-HBs, who have known bridging fibrosis or cirrhosis, should be considered on a case by case basis.

Figure 3-1. Study Schema

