4. SUBJECT POPULATION

4.1. Number of Subjects and Subject Selection

Approximately 390 subjects, who are 18 years of age and older, with HBeAg-negative chronic hepatitis B will be randomized 2:1 to receive either blinded TAF 25 mg and TDF 300 mg matched placebo (n = 260) or TDF 300 mg and TAF 25 mg matched placebo (n = 130) for 144 weeks (96 weeks under Amendment 2.1).

For China, approximately 150 subjects, who are 18 years of age and older, with HBeAg-negative chronic hepatitis B will be randomized 2:1 to receive either blinded TAF 25 mg and TDF 300 mg matched placebo (n = 100) or TDF 300 mg and TAF 25 mg matched placebo (n = 50) for 96 weeks.

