5.3. Dosage and Administration of TAF and TDF and Matched Placebos

Subjects will be randomly assigned (2:1) to receive one of the following treatments in a blinded fashion:

Treatment Arm A: 260 subjects TAF 25 mg QD and matched placebo of TDF 300 mg QD

Treatment Arm B: 130 subjects TDF 300 mg QD and matched placebo of TAF 25 mg QD

For China, approximately 150 additional subjects will be randomized 2:1 to receive either Treatment A (n = 100) or Treatment B (n = 50) for 144 weeks.

After 144 weeks of blinded randomized treatment (96 weeks under Amendment 2.1), each subject will switch to open-label TAF 25 mg QD for up to an additional 240 weeks (Week 144 through Week 384/ED). Subjects already assigned to open-label TAF 25 mg QD at Week 96 per Amendment 2.1 will continue on TAF through Week 384/ED.

It is preferred that subjects take their study drug according to a morning dosing schedule; however, evening dosing is allowable.

All study drugs should be taken at approximately the same time each day with food.

Observed in-clinic study drug dosing is required at Weeks 4 and 12 visits. Subjects who elect to dose in evening are not required to have in-clinic dosing and the single PK blood sample collection at the Week 4 and 12 visits.

Study drug should be administered after assessing adverse events and concomitant medication(s).

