Fasting Urine for Renal Biomarkers ⁱ		X		X		X		X		X	
Fasting Metabolic Panel ^j		X		X		X		X		X	
Urine Pregnancy Test ^k	X	X	X	X	X	X	X	X	X	X	X

Visit windows	Week										
	168	192	216	240	264	288	312	336	360	384/ED ^o	FU ^p
	±28 days										
Urinalysis	X	X	X	X	X	X	X	X	X	X	X
Serum and plasma for storage	X	X	X	X	X	X	X	X	X	X	X (serum only)
Urine for Storage	X	X	X	X	X	X	X	X	X	X	
Ophthalmologic substudy ⁿ – fundoscopic examination with slit lamp										X ⁿ	
Hepatic Ultrasound ^f	X	X	X	X	X	X	X	X	X	X	

- a The visit window for Week 48 visit is –14 days. The visit window for Week 96 is ±14 days.
- b Subjects must rest quietly in the supine position for a minimum of 5 minutes prior to the recording
- c Vital signs include blood pressure, pulse, respiration rate, and temperature
- d DXA scans will be performed only at sites in China with capability. The initial (baseline) DXA will be performed during Screening and should be completed at least 14 days prior to the first dose of study drug. The Week 48 DXA window is –14 days only. DXA is required for Early Discontinuation (ED) visit if not done within the last 24 weeks. Subjects already assigned to open-label TAF 25 mg QD per Amend 2.1 continue on open-label TAF 25 mg QD. Otherwise, blinded study drug will be dispensed until Week 144 visit. Open label TAF will be dispensed from Week 144 through Week 360. At Week 384/ED, study drug will not be dispensed
- f It is preferred that subjects take their study drug according to a morning dosing schedule; subjects who elect to dose in the evening the previous day are not required to have in-clinic dosing and provide the single PK sample being collected at Week 4 and 12 visits.
- g Serum chemistry and Liver Function Tests : alkaline phosphatase, AST, ALT, GGT, total bilirubin, direct and indirect bilirubin, total protein, albumin, LDH, CPK, bicarbonate, BUN, calcium, chloride, creatinine, glucose, phosphorus, magnesium, potassium, sodium, uric acid, and amylase (reflex lipase testing is performed in subjects with total amylase > 1.5 × ULN), and PTH. PTH analyzed at all visits except for Screening through Week 96, and then at Weeks 120, 144, and then every 48 weeks through Week 384/ED. At Baseline, Weeks 24, 48, 72, 96, 120, 144, 192, 240, 288, 336 and 384/ED, subject will be fasting for serum and glucose and metabolic panel. Coagulation panel will be done at Screening and then as a reflex only test for ALT flares.

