1. INTRODUCTION

GS-US-320-0108 is a randomized, double-blind, noninferiority study to compare the antiviral activity of tenofovir alafenamide (TAF) 25 mg once daily versus tenofovir disoproxil fumarate (TDF) 300 mg once daily for the treatment of HBeAg-negative, chronic hepatitis B (CHB) in treatment-naïve and treatment-experienced subjects. For non-China part, 426 subjects were randomized in a 2:1 ratio to the treatment groups, and were stratified by plasma hepatitis B virus (HBV) DNA level ($< 7 \log_{10}$ IU/mL, $\geq 7 \log_{10}$ IU/mL - $< 8 \log_{10}$ IU/mL, $\geq 8 \log_{10}$ IU/mL) and oral antiviral treatment status (treatment-naïve vs treatment-experienced).

Treatment-naïve subjects are defined as subjects with < 12 weeks of previous oral antiviral treatment with any nucleoside or nucleotide analogue. Treatment-experienced subjects are defined as subjects with ≥ 12 weeks of previous treatment with any nucleoside or nucleotide analogue.

For China, approximately 150 additional subjects (100 in TAF group and 50 in TDF group) will be enrolled for local registration purposes.

The duration of double-blind treatment is 144 weeks (96 weeks under Amendment 1 and 2.1). All subjects who complete the double-blind period of treatment are eligible for participation in the open label TAF 25 mg extension period for an additional 240 weeks (through Week 384/ED). Subjects who already entered open label phase at Week 96 per Amendment 2.1 will continue on open label TAF 25 mg QD through Week 384/ED. For the entire duration of the study, subjects and investigators will remain blinded to the initial treatment regimen to which they were randomized.

This statistical analysis plan (SAP) describes the analysis plan for the Week 48 analysis of subjects enrolled in China only.

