Follow-up assessments will occur every 4 weeks for 24 weeks and include the following: vital signs, hematology, serum chemistry, liver function tests, and plasma HBV DNA. Plasma, serum and urine will be collected for storage. HBsAg and reflex HBsAb will be evaluated at follow-up Weeks 12 and 24.

Ophthalmologic Substudy

For subjects who provide a separate informed consent (n = 30), a substudy will be conducted to assess ophthalmologic findings, including a fundoscopic examination with slit lamp and retinal photographs (both eyes) prior to the first dose of study drug and at Weeks 24, 48, 72, 96, and 144/ED visits at select sites. An exam should be performed at the ED visit if it is prior to Week 144 and not done within the last 24 weeks of this visit.

Randomization

Subjects will be randomized in a 2:1 ratio to the 2 treatment groups (TAF vs TDF, respectively). Randomization will be stratified by plasma HBV DNA level ($< 7 \log_{10}$ IU/mL, $\geq 7 \log_{10}$ IU/mL - $< 8 \log_{10}$ IU/mL, $\geq 8 \log_{10}$ IU/mL) and oral antiviral treatment status (treatment-naïve vs treatment-experienced).

Site and/or Stratum Enrollment Limits

Twenty-nine centers participated in China. There is no enrollment limit for individual sites.

Study Duration

The duration of the double-blind treatment is 144 weeks (96 weeks under Amendment 1 and 2.1). All subjects who complete the double-blind period of treatment are eligible for participation in the open label TAF 25 mg extension period for an additional 240 weeks (through Week 384/ED). Subjects already assigned to open label TAF 25 mg QD at Week 96 per Amendment 2.1 will continue on open label TAF 25 mg QD through Week 384/ED. Subjects who permanently discontinue study drug (either prematurely [ED] or at the end of study [Week 384]) for reasons other than HBsAg loss with confirmed seroconversion to anti-HBs will be followed every 4 weeks for 24 weeks off treatment or until initiation of alternative, commercially available HBV therapy, whichever occurs first. All subjects in China are currently enrolled under Amendment 3.1 and will complete 3 years of double-blind treatment before rolling over to open-label TAF 25 mg once daily.

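### Protocol Sections 3.1 and 4.1 give the China cohort 96 weeks of blinded treatment; Protocol Section 5.3 gives 144 weeks and SAP Section 1.2 gives 3 years

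*Protocol*

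**What the plan says.** Four statements address the blinded duration of the China cohort directly.

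- Protocol 3.1 (Treatment Plan and Regimen): "For China, approximately 150 additional subjects will be randomized in a 2:1 ratio (A: B) to the treatment arms for 96 weeks".
- Protocol 4.1 (Number of Subjects and Subject Selection), for the China TDF arm: "TDF 300 mg and TAF 25 mg matched placebo (n = 50) for 96 weeks".
- Protocol 5.3 (Dosage and Administration), for China: "additional subjects will be randomized 2:1 to receive either Treatment A (n = 100) or Treatment B (n = 50) for 144 weeks".
- SAP 1.2 (Study Duration): "All subjects in China are currently enrolled under Amendment 3.1 and will complete 3 years of double-blind treatment".

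The general text is as follows. Protocol 3.1 and 5.1 set 144 blinded weeks, with 96 weeks only under Amendment 2.1, followed by a switch to open-label TAF. The dispensing footnote in Appendix 2 excepts subjects already on open-label TAF under Amendment 2.1 and then says: "Otherwise, blinded study drug will be dispensed until Week 144 visit". SAP Section 1 confines 96 weeks to Amendments 1 and 2.1, and the open-label objective in SAP 1.1 links Amendment 3.1 to a switch at Week 144. The protocol synopsis gives China numbers but no China-specific duration.

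**The concern.** One protocol gives one cohort two blinded durations. The 96-week figure does not read as an obvious slip. In both 3.1 and 4.1 the main-cohort sentence gives 144 weeks with 96 in brackets for Amendment 2.1, and the China sentence that follows gives a bare 96. A site could reasonably take it as a China-specific rule standing beside the general one. The Amendment 2.1 exception cannot explain it, because SAP 1.2 puts all China subjects under Amendment 3.1.

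If 3.1 and 4.1 were acted on, China TDF subjects would move to open-label TAF at Week 96, and that cannot be undone. After that there would be no concurrent TDF arm in China for the Week 144 comparisons listed among the objectives, or for the Week 120 and 144 DXA scans, which this protocol version schedules only at China sites with capability. The end of the blinded period also sets when the renal dose-modification rule (Protocol 7.5.5) ceases to apply and when DMC meetings move from every 24 to every 48 weeks (Protocol 8.9).

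**Working it through.** No power formula is involved. The check sets the passages side by side and does the week arithmetic.

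**1. Passages compared**

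| Place | Covers | Blinded duration |
|---|---|---|
| Protocol 3.1, China sentence | China | 96 weeks, unqualified |
| Protocol 4.1, China sentence | China, 100 + 50 | 96 weeks, unqualified |
| Protocol 5.3, China sentence | China, 100 + 50 | 144 weeks |
| SAP 1.2 | China | 3 years, all under Amendment 3.1 |
| Protocol 3.1 and 5.1, general rule | All | 144 weeks; 96 under Amendment 2.1 |
| Protocol 6.3.1.9, 6.3.1.11, 6.3.1.12 | All | Blinded drug dispensed at Weeks 96, 108, 120 and 132 (Amendment 2.1 switchers excepted after Week 96); open-label TAF for everyone at Week 144 |
| Protocol Appendix 2, dispensing footnote | All | Blinded to Week 144 unless already switched under Amendment 2.1 |
| SAP 1 and 1.1 | All | 96 weeks only under Amendments 1 and 2.1; Amendment 3.1 tied to Week 144 |

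**2. The plan's own extension length.** Protocol 3.1 gives an open-label extension of up to 240 weeks, ending at Week 384.

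- With 144 blinded weeks: 384 - 144 = 240. This reproduces the stated figure.
- With 96 blinded weeks: 384 - 96 = 288. This does not.

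**3. Is 3 years a third duration?** 144/48 = 3.0 study years of 48 weeks. In calendar time, 144 x 7/365.25 = 2.76 years, and three calendar years are 3 x 365.25/7 = 156.5 weeks, which appears nowhere in the plan. The SAP wording is loose but fits 144 weeks. There are two durations in conflict, not three.

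**4. Size of the disputed interval.** 144 - 96 = 48 weeks. For 50 TDF subjects: 50 x 48/52 = 46.2, about 46 patient-years. This is an upper limit, since it assumes all 50 remain on blinded TDF from Week 96 to Week 144.

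**5. Reach into the planned China analysis.** Protocol 8.5.2 and SAP 2 plan the China analysis at Week 48. The primary and key secondary endpoints are at or through Week 48. SAP 6.2.1 leaves efficacy endpoints beyond Week 96 out of this analysis, and SAP 7 summarises safety only up to Week 96. One small edge remains: cumulative safety summaries are cut at Study Day 839, which is 839 - 672 = 167 days after nominal Week 96. The documents do not say whether any China subject had passed Week 96 by the data cut.

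**The case against.** The strongest reply is that the documents, read together, are not evenly split. The SAP was written for the China cohort, and it states as a fact of enrolment that all its subjects are under Amendment 3.1. It ties that amendment to Week 144. The general rule, the visit-by-visit dispensing instructions, the Appendix 2 footnote and the 240-week extension agree with it. No visit instruction tells a site to switch anyone newly at Week 96, and treatment is assigned centrally through the IVRS/IWRS. This stands, and it rules out several stronger readings.

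- A reader might infer that it is undetermined whether blinded Week 96 to 144 data will exist. That goes too far: the 96-week sentences in 3.1 and 4.1 are the outliers.
- A reader might infer an IWRS or drug-supply error. The documents show none. A check is prudent, but a mismatch is not established.
- A reader might count HBV DNA and ALT comparisons at Week 120 among the losses. Week 120 is not a listed time point for those endpoints.
- A reader might want the SAP visit windows revised. They are keyed to study day, run on to Week 384 and work under either duration.

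The reply does not remove the contradiction. Two explicit, cohort-specific sentences in the design and population sections remain. Sites work to the protocol, and a SAP sentence does not instruct them.

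**Conclusion.** The contradiction is real and lies in current text: Protocol 3.1 and 4.1 against Protocol 5.3 and SAP 1.2. It is a document inconsistency with a possible irreversible effect, not a flaw in the design. The China Week 48 primary and key secondary results do not depend on it. What does depend on it is a concurrent TDF arm over 48 weeks, worth at most about 46 patient-years if all 50 planned TDF subjects are enrolled and none drops out. The DXA share is smaller by an unknown amount, because only China sites with capability scan. The conclusion rests on reading the SAP's 3 years as three 48-week years, and on the enrolment statement in SAP 1.2 being accurate. It takes no position on which duration should apply. That is for the sponsor to state.

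**What to change.** The sponsor should state one blinded duration for the China cohort and bring Protocol 3.1, 4.1 and 5.3 and SAP 1.2 into line with it, by clarification letter or administrative amendment. SAP 1.2 should express the duration in weeks. The sponsor should also confirm that the IWRS switch visit and drug supply for China match the stated duration. This should be done before any China subject reaches Week 96. If some already have, their actual treatment from Week 96 should be verified and recorded. The cost is a short document and one system check. Sample size, endpoints and SAP analysis windows stay as they are.
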